1.1 Salivary Gland Carcinoma

Salivary gland cancers (SGC) are rare neoplasms, constituting approximately 5% of head and neck cancers, with an overall incidence of 1-3 per 100,000 persons. There are multiple histological subtypes including adenoid cystic carcinoma, mucoepidermoid carcinoma, and adenocarcinoma. The biologic behavior of these cancers is quite variable [Laurie]. Initial therapy for patients who present with localized disease consists of surgery and/or radiation therapy. Neutron beam radiotherapy has been demonstrated to have superior efficacy to conventional radiotherapy for the treatment of localized disease [Griffin]. As the University of Washington is one of only a few neutron facilities operating worldwide, it has become a referral center for the treatment of this rare neoplasm. Despite optimal treatment, many patients progress either locally or with distant metastatic disease. Due to the rare nature of this disease, conducting clinical trials is difficult; therefore there is limited clinical trial data to guide systemic therapeutic treatments.

1.2 Systemic therapy for advanced refractory and metastatic SGC

There is no current standard of care for palliative chemotherapy in patients with advanced SGC. A recent review cited 12 small trials reporting the use of chemotherapy for salivary gland carcinomas [Laurie]. In general, objective responses to any cytotoxic agent or regimen are infrequent and stabilization of disease is more commonly observed. Agents with activity include cisplatin, mitoxantrone, vinorelbine, epirubicin, and paclitaxel. Combination chemotherapy also appears to be effective. The only randomized clinical trial done in this cancer demonstrated a higher response rate with cisplatin and vinorelbine compared to vinorelbine alone [Airoldi]. Data is insufficient to conclude that combination chemotherapy is superior to single agent therapy and combination therapy certainly has more toxicity. Despite scientific rationale for the use of molecular targeted agents such as imatinib (c-kit) [Hotte], gefitinib (EGFR), and trastuzumab (HER2) [Agulnik], the results of these agents in phase II clinical trials have been disappointing.

5.1 Inclusion Criteria

Patients are eligible to be included in the study only if they meet all of the following criteria:

- Patients must have histologically or cytologically documented salivary gland cancers. Patients that do not have a salivary gland primary must have one of the following histologies - adenoid cystic carcinoma, mucoepidermoid carcinoma, acinic cell carcinoma).
- Patients must have recurrent and/or metastatic disease that is progressive and not amenable to surgery or curative radiotherapy occurring within 6 months of study entry, as evidenced by: at least a 20% increase in radiographically or clinically measurable disease, appearance of any new lesions, or deterioration in clinical status.
- Age \geq 18 years.
- ECOG performance status of 0, 1, or 2.
- Patients with measurable disease per RECIST 1.1 criteria [Eisenhauer].
 - At least one lesion of \geq 1.5 cm in long-axis diameter for nonlymph nodes or \geq 1.5 cm in short-axis diameter for lymph nodes which is serially measurable according to RECIST 1.1 using either computerized tomography (CT) or magnetic resonance imaging (MRI).
 - Lesions that have had radiotherapy must show evidence of progressive disease (PD) based on RECIST 1.1 to be deemed a target lesion.
- Patients must have normal organ and marrow function as defined below:
 - absolute neutrophil count \geq 1,500/ μ L
 - platelets \geq 100,000/ μ L
 - creatinine clearance \geq 40 mL/min
 - bilirubin \leq 1.5 ULN
 - Alkaline phosphatase \leq 3 ULN. If total ALP is $>$ 3 x ULN (in the absence of liver metastasis) or $>$ 5 x ULN in subjects with liver metastasis AND the subject is known to have bone metastases, then liver ALP iso-enzyme should be used to assess liver function rather than total ALP.
 - AST and ALT \leq 3 X ULN,
- Women of child-bearing potential (WOCP) and men must agree to use adequate contraception (hormonal or barrier method of birth control or abstinence) prior to study entry and for the duration of study participation.
- Life expectancy of $>$ 12 weeks.
- Signed and dated informed consent document indicating that the patient has been informed of all the pertinent aspects of the trial prior to enrollment.

5.2 Exclusion Criteria

Subjects presenting with any of the following will not be included in the trial:

- Patients with symptomatic CNS metastases must have stable disease after

treatment with surgery or radiation therapy.

- Second primary malignancy that is clinically detectable or clinically significant at the time of consideration for study enrollment
- Radiotherapy within 14 days of study treatment.
- Major surgery within 21 days of study treatment. Minor surgery within 2 weeks of study treatment. Placement of vascular access device and biopsies allowed and is not considered major or minor surgery.
- Treatment with any chemotherapy or investigational agents within 4 weeks of the start of study treatment. Subjects must have recovered from toxicities of prior therapy.
- Patients with peripheral neuropathy \geq grade 2
- Significant cardiovascular impairment: congestive heart failure >Class II according to the New York Heart Association (NYHA), unstable angina or myocardial infarction within 6 months of enrollment, or serious cardiac arrhythmia (> grade 2).
- Concomitant severe or uncontrolled medical disease.
- Significant psychiatric or neurologic disorder which would compromise participation in the study
- Pregnant or breast-feeding females.

6. *Trial Treatments*

All patients enrolled will receive treatment with eribulin.

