7.1 Screening Visit

The screening visit will occur up to 30 days prior to initiating study treatment.

- Medical History - SGC diagnosis, prior SGC treatment history, and demographics.
- Physical examination - examination of major organ systems, ECOG performance status, body weight and vital signs (i.e., blood pressure, heart rate).
- Laboratory Evaluations will be obtained up to 14 days prior the first dose of eribulin
 - Hematology (CBC with platelets and absolute neutrophil count)
 - Blood chemistry (sodium, potassium, chloride, carbon dioxide, creatinine, BUN, glucose, calcium, LDH, albumin, bilirubin, AST, ALT, total protein, alkaline phosphatase, magnesium)

- Pregnancy test - serum or urine pregnancy test performed for all women of childbearing potential
- CT scan for known sites of involvement.
- ECG If < 450, no further monitoring. If > 450, needs ECG prior to second dose of eribulin. If > 480, eribulin needs to be held until QTc value is within protocol specified range.

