8.1 Efficacy Assessments

Patients will have their tumors assessed for response by conventional imaging methods (typically CT scans), which will be performed at baseline (at least 30 days prior to the first study drug dose) and then at least every 2 cycles (~ every 6 weeks) after initial dose. Once patients have completed 4 cycles of therapy, they can have CT scans after every 3 cycles.

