8.1.2 Baseline Documentation of Tumor Burden

- Target lesions: All measurable lesions should be identified and recorded and measured at baseline. Target lesions should be selected on the basis of their size (those with the longest diameter) and their suitability for accurate repeated measurements (either by imaging techniques or clinically). A sum of the longest diameter for all target lesions will be calculated and reported as the baseline sum longest diameter (SLD). The baseline SLD will be used as the reference by which to characterize the objective tumor response.
- Non-target lesions: All other lesions (or sites of disease) should be identified as non-target lesions and should also be recorded at baseline. Measurements of these lesions are not required, but the presence or absence of each should be noted throughout follow-up.

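### The baseline scan is not tied to the end of earlier local treatment, so shrinkage from pre-dose radiotherapy or surgery can be scored as a response to eribulin (low priority)

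*Combined protocol and SAP*

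**What the plan says.** **Timing of the scan.** Section 7.1, which lists the CT among the screening procedures, says: "The screening visit will occur up to 30 days prior to initiating study treatment". Appendix 1 also places the CT in its 30-day screening column. Section 8.1 says something different: imaging is "performed at baseline (at least 30 days prior to the first study drug dose". Sections 7.2 and 8.1 and Appendix 1 put the next CT after cycle 2.

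**Washouts.** Section 5.2 excludes "Radiotherapy within 14 days of study treatment" and, for surgery, "Major surgery within 21 days of study treatment. Minor surgery within 2 weeks of study treatment". Biopsies and vascular access devices do not count as surgery. Chemotherapy and investigational agents have a 4-week washout. Every interval is counted from study treatment.

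**Reference for response.** Section 8.1.2 states: "The baseline SLD will be used as the reference by which to characterize the objective tumor response". Section 8.1.3 defines a partial response as a fall of at least 30% in the summed target-lesion diameters and makes no exception for locally treated lesions.

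**Existing safeguards.** Section 5.1 has a rule for irradiated lesions: "Lesions that have had radiotherapy must show evidence of progressive disease (PD) based on RECIST 1.1 to be deemed a target lesion". It also restricts entry to progressive disease for which surgery or curative radiation is not an option. No section requires the baseline scan to follow earlier local treatment or to be repeated after it.

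**The concern.** The scan window is longer than the radiotherapy and surgery washouts, and nothing links the two. A patient can be scanned, then irradiated or operated on, then dosed, and still meet every timing rule. The reference sum would then describe the tumor before the local treatment, and the first scan on study would show the effect of that treatment together with any effect of eribulin.

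The primary endpoint is the response rate in a single arm, so there is no comparator against which such an effect would cancel out. The decision rule in Section 10.1 works on very few events: one response among 10 opens the second stage, and four among 29 is a positive result. A single misattributed response is therefore a meaningful share of what the trial needs.

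**Working it through.** **1. Gap in days.** Gap = earliest permitted scan (30 days before dosing, Section 7.1) minus washout (Section 5.2).

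| Treatment | Washout (days) | Gap (days) |
|---|---|---|
| Radiotherapy | 14 | 30 - 14 = 16 |
| Minor surgery | 14 | 30 - 14 = 16 |
| Major surgery | 21 | 30 - 21 = 9 |
| Chemotherapy, investigational agents | 28 | 30 - 28 = 2 |

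Read literally, Section 8.1 puts the scan at day -30 or earlier, so it would always precede the whole of each gap.

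**2. What the Section 5.1 rule on irradiated lesions covers.** Read plainly, a lesion irradiated between the scan and the first dose has had radiotherapy. Without shown progression it is not a target lesion, and its shrinkage stays out of the sum. Two things are left open:
- The rule does not say that progression must be shown after that radiotherapy. Entry already requires progressive disease, so earlier progression could be taken to satisfy it.
- It does not say what happens to a lesion chosen from the scan and irradiated afterwards, and no further scan is scheduled before dosing.

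The rule does not mention surgery.

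**3. What a false partial response looks like.** The sizes here are illustrative and not from the documents. Baseline sum 60 mm; one 30 mm lesion, kept as a target, shrinks to 10 mm from local treatment; the rest is unchanged. The new sum is 40 mm, and the fall is 20/60 = 33%, which exceeds 30%.

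**4. The plan's own design figures.** From Section 10.1: n1 = 10, stop at 0 responses; N = 29, success at 4 or more; p0 = 0.05, p1 = 0.20.
- Early stopping at p0: 0.95^10 = 0.599 (plan: 0.60).
- Expected N at p0: 10 + (1 - 0.599) × 19 = 17.6 (plan: 17.6).
- P(success) = sum over x = 1 to 10 of P(X1 = x) × P(X2 ≥ 4 - x), with X1 ~ Bin(10, p) and X2 ~ Bin(19, p). This gives 0.0468 at p = 0.05 and 0.801 at p = 0.20.

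The design reproduces.

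**5. One false response taken as certain, true rate 5%.**
- In stage 1: the first stage is passed automatically, and 3 or more responses are needed from the other 28. P(Bin(28, 0.05) ≥ 3) = 1 - (0.2378 + 0.3505 + 0.2490) = 0.163.
- In stage 2: stage 1 must still be passed by a real response. 0.1627 - 0.5987 × P(Bin(18, 0.05) ≥ 3) = 0.1627 - 0.5987 × 0.0581 = 0.128.
- Averaged over position: (10/29) × 0.163 + (19/29) × 0.128 = 0.140.
- Two certain false responses, averaged over position: 0.342.

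**6. Without assuming that it happens.** Suppose one patient is exposed and has chance f of a false response. P(success) = (1 - f) × 0.0468 + f × (0.128 or 0.163). The values of f are assumptions.
- f = 0: 4.7%, unchanged.
- f = 0.10: 5.5% to 5.8%.
- f = 0.25: 6.7% to 7.6%.

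**The case against.** The best defense is that the plan already deals with most of this. The Section 5.1 rule, plainly read, keeps a freshly irradiated lesion out of the target set. Disease not suited to surgery is an entry condition, so removal of target disease making up 30% of the sum, between the screening scan and the first dose, should be unusual. Biopsies would rarely produce such a fall. The chemotherapy gap is two days at most. Section 1.1 describes the center as a neutron referral site for localized disease, which does not show that patients in this trial are irradiated between scan and dosing. Section 7.1 records prior treatment, and with a single center the team would probably know of a recent local procedure.

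Most of this stands, and it limits how often the problem could arise. It does not remove the gap. Palliative radiotherapy and palliative excision before entry are not barred outside the washouts. Knowing of a procedure is also different from having a rule for scoring it, and none is given.

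A reader might infer that shrinkage from pre-dose local treatment *is* counted as response under this plan. The documents do not support that: they leave it possible for an irradiated lesion only on a strained or incomplete reading of Section 5.1, and for a resected lesion only in an uncommon sequence.

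**Conclusion.** The gap is real: the baseline sum can predate radiotherapy or surgery by a sequence that breaks no written timing rule, and the resulting shrinkage can be scored as a response. Sections 7.1 and 8.1 also contradict each other on when the baseline scan is taken.

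The size is conditional. If one false response occurs and the true rate is 5%, the probability of a wrong positive conclusion goes from 4.7% to about 13-16%, depending on the stage. It would be a mistake to read 13-16% as the trial's actual type I error. That figure presumes that the false response has happened, and the documents give no frequency. A count of 0 to 2 among 29 is my assumption, and at 0 nothing changes. Given the safeguards in Section 5.1, the frequency is probably low. This is a low-priority clarification, worth making because it is cheap and protects the primary endpoint.

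**What to change.** - **Sections 7.1 and 8.1:** reconcile the two so that both place the baseline tumor scan within 30 days before the first dose.
- **Same sections:** require that scan to follow completion of the last radiotherapy, tumor surgery or systemic anticancer treatment; otherwise it is repeated before dosing.
- **Section 5.1:** state that progression of an irradiated lesion must be shown on imaging obtained after that radiotherapy.
- **Section 8.1.2:** state that a lesion irradiated or removed after the baseline scan and before the first dose is not a target lesion, and is left out of the baseline sum unless the scan is repeated.

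The cost is a few sentences in an amendment and an occasional re-timed or repeated CT. The washouts, the treatment rules and the two-stage design stay as they are.

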6.1 Drug Supplies

6.1.1 Formulation and Packaging

Eribulin mesylate will be supplied by Eisai in single-use vials at a concentration of 1 mg/2 mL (0.5 mg/mL) solution in ethanol: water (5:95). Eribulin is a clear, colorless, sterile solution for intravenous administration.

6.1.2 Preparation and Dispensing

Aseptically withdraw the required amount of eribulin mesylate from the single-use vial and administer undiluted or diluted in 100 mL of 0.9% Sodium Chloride Injection, USP. **Do not dilute in or administer through an intravenous line containing solutions with dextrose.** Do not administer in the same intravenous line concurrent with the other medicinal products.

Store undiluted eribulin mesylate in the syringe for up to 4 hours at room temperature or for up to 24 hours under refrigeration (40°F or/ 4°C). Store diluted solutions of eribulin mesylate for up to 4 hours at room temperature or up to 24 hours under refrigeration.

Discard unused portions of the vial.

6.2 Treating the Patient

6.2.1 Conditions patients must meet prior to administering any treatment on Day 1 and 8 of each cycle

Prior to receiving any study treatment on Day 1 or 8 of each cycle, the patient must have all of the following criteria met:

- Neutrophils are $\geq 1.0 \times 10^9/L$,
- Platelets $\geq 75 \times 10^9/L$,
- No grade 3 or 4 non-hematological toxicities.

The Day 8 dose may be delayed for a maximum of 1 week.

- If toxicities do not resolve or improve to \leq Grade 2 severity by Day 15, omit the dose.
- If toxicities resolve or improve to \leq Grade 2 severity by Day 15, administer eribulin at a reduced dose and initiate the next cycle no sooner than 2 weeks later.

Blood tests should be performed before starting any study treatment administration and if the above criteria are not met, treatment should be delayed until the criteria for start of treatment are met. If a delay of > 3 weeks (one cycle) is required, the patient should be removed from the study and continue to be treated in accordance with the Investigator's standard clinical practice.

6.2.2 Eribulin administration

Patients will receive eribulin 1.4 mg/m^2 administered intravenously (IV push) over 2 to 5 minutes on Days 1 and 8 of a 21-day cycle. Treatment will be continued until disease progression, unacceptable toxicity or patient withdraws consent.

Guidelines for dose modification and dose interruption of study drug are described in Table 6-1.

6.2.3 Dose Modifications

Any dose reduction or dose delay of study drug is based upon the severity of toxicity, as graded by NCI Clinical Toxicity Criteria (NCI-CTCAE, version 4.0). Once a dose has been reduced during a treatment cycle, re-escalation will not be permitted during any subsequent cycles.

All toxicity-related causes for dose reductions or dose delays, must be recorded as an AE. Please refer to Table 6-1 for recommended study drug dose adjustments. Patients requiring a delay in study treatment > 3 weeks or > 2 dose reductions, will be discontinued from study treatment.

Table 6-1 Recommended Dose Reductions of Eribulin

Event Description	Recommended Dose
Permanently reduce the dose for any of the following: 
 • ANC <500/mm³ for >7 days • ANC <1,000 /mm³ with fever or infection • Platelets <25,000/mm³ • Platelets <50,000/mm³ requiring transfusion • Non-hematologic Grade 3 or 4 toxicities • Omission or delay of Day 8 dose in previous cycle for toxicity • Creatinine clearance 30-50 mL/min • ECG > 480 hold drug until QTc value is within protocol specified range. 	1.1 mg/m ²
Occurrence of any event requiring permanent dose reduction while receiving 1.1 mg/m²	0.7 mg/m ²
Occurrence of any event requiring permanent dose reduction while receiving 0.7 mg/m² or a Creatinine clearance <30 mL/min	Discontinue eribulin

6.3 Concomitant Medications

Concomitant therapies considered as supportive care are acceptable while participating in this study including granulocyte colony stimulating factors (GCSF), palliative radiation and bisphosphonates for bone metastasis. Patients that require palliative radiation should wait 7-14 days before resuming eribulin therapy.

7. Trial Procedures

Prior to undergoing any study-specific procedure, patients must read and sign the current Institutional Review Board (IRB)-approved informed consent form.

The schedule of assessments is presented in Table 1 (Visit Schedule) in the Protocol Summary.

Assessments outlined in the visit schedule include the following components:

7.1 Screening Visit

The screening visit will occur up to 30 days prior to initiating study treatment.

- Medical History - SGC diagnosis, prior SGC treatment history, and demographics.
- Physical examination - examination of major organ systems, ECOG performance status, body weight and vital signs (i.e., blood pressure, heart rate).
- Laboratory Evaluations will be obtained up to 14 days prior the first dose of eribulin
 - Hematology (CBC with platelets and absolute neutrophil count)
 - Blood chemistry (sodium, potassium, chloride, carbon dioxide, creatinine, BUN, glucose, calcium, LDH, albumin, bilirubin, AST, ALT, total protein, alkaline phosphatase, magnesium)

- Pregnancy test - serum or urine pregnancy test performed for all women of childbearing potential
- CT scan for known sites of involvement.
- ECG If < 450, no further monitoring. If > 450, needs ECG prior to second dose of eribulin. If > 480, eribulin needs to be held until QTc value is within protocol specified range.

7.2 Day 1 of each Cycle

Day 1 will occur every 21 days (+/- 4 days)

- Physical examination - examination of major organ systems, ECOG performance status, body weight and vital signs (i.e., blood pressure, heart rate).
- Laboratory Evaluations
 - Hematology (CBC with platelets and absolute neutrophil count)
 - Blood chemistry (sodium, potassium, chloride, carbon dioxide, creatinine, BUN, glucose, calcium, LDH, albumin, bilirubin, AST, ALT, total protein, alkaline phosphatase, magnesium)
- Adverse Event Assessment
- CT scan for known sites of involvement after every 2 cycles (i.e. after cycle 2, 4, 6, etc. Once patients have completed 4 cycles of therapy, they can have CT scans after every 3 cycles.)

7.3 End of Treatment Visit

Patients will undergo the following assessments when all study treatment is discontinued:

- Physical examination - examination of major organ systems, ECOG performance status, body weight and vital signs (i.e., blood pressure, heart rate).
- Laboratory Evaluations
 - Hematology (CBC with platelets and absolute neutrophil count)
 - Blood chemistry (sodium, potassium, chloride, carbon dioxide, creatinine, BUN, glucose, calcium, LDH, albumin, bilirubin, AST, ALT, total protein, alkaline phosphatase, magnesium)
- Adverse Event Assessment

7.4 Thirty Day Post Treatment Visit

Patients will undergo evaluation for toxicity 30 days (+/- 6 days) after the last dose of study treatment. Patients will undergo the following assessments:

- Physical examination - examination of major organ systems, ECOG performance status, body weight and vital signs (i.e., blood pressure, heart rate).
- Laboratory Evaluations
 - Hematology (CBC with platelets and absolute neutrophil count)
 - Blood chemistry (sodium, potassium, chloride, carbon dioxide, creatinine, BUN, glucose, calcium, LDH, albumin, bilirubin, AST, ALT, total protein, alkaline phosphatase, magnesium)
- Adverse Event Assessment

7.5 Subject Withdrawal

Patients will be removed from study if they present with disease progression, as defined by radiological RECIST 1.1 criteria. Subjects will also be removed from study if they require more than two dose level reductions. Subjects will also be removed from study if they require more than 3 weeks to recover from adverse events. Patients may withdraw consent at any time.

8. Assessments

The schedule of assessments is presented in Appendix 1. The description of assessments is provided in Section 7.

